6.1 Study Monitoring Plan

The study PI will be responsible for ensuring the ongoing quality and integrity of the research study.

CONFIDENTIAL

6.2 Auditing and Inspecting

The Investigator will permit study-related monitoring, audits, and inspections by the IRB, the sponsor, government regulatory bodies, and University compliance and quality assurance groups of all study related documents (e.g. source documents, regulatory documents, data collection instruments, study data etc).

7 Ethical Considerations

The protocol, amendments and continuing reviews will be submitted for review by the Penn IRB and other appropriate reviewing entities.

7.1 Risks

There are minor risks to subjects who choose to participate in the study. The ultrasound examination, breath collection, arterial tonometry, NIRS, thermal imaging, and sublingual capillaroscopy have no known risks.

Venipuncture: According to the 2010 WHO guidelines on phlebotomy, major risks associated with venipuncture include hematoma at the site of venipuncture in 2-3%, and vasovagal reactions and fainting in 1%.

Endothelial cell harvesting: The risks associated with the procurement of venous endothelial cells are low and are analogous to the risks that occur with placement of a venous catheter, which include pain, superficial phlebitis/venous blood clots and infection.

During various procedures (echocardiography, arterial tonometry), we will use adhesive electrodes attached to the participant's skin to record the electrical signal from the heart. These may occasionally cause skin itching and irritation.

Risks of pulmonary function tests: Our pulmonary function tests will not involve challenging (such as methacholine administration) and thus are very low risk. A potential risk is dizziness during forced maneuvers or shortness of breath during the 8-10 breath hold required for DLCO measurements. The tests may rarely cause sore chest muscles. There is a very low risk of pneumothorax from forced expiration.

Risks of exercise testing: This test is used extensively for research purposes with minimal risk to subjects. The most significant risks of the test are dysrhythmias or other cardiovascular complications, which are extremely rare. These procedures will be performed by qualified personnel according to established American Heart Association Guidelines.^{135,136} Non-revascularized myocardial ischemia, which may increase the risk of complications during exercise testing, is an exclusion criterion for the study. Furthermore, the procedure is voluntary and intended to only be performed in a subset of participants in the study and will not be performed in any participants with a contraindication to exercise, such as elevated risk of falls (as assessed by the investigators) or severely elevated blood pressure (>180/100).

Subjects may feel uncomfortable as a result of pushing themselves during the maximal effort exercise test. Subjects will likely feel short of breath and fatigued as a result of the exercise test. Various other complaints, such as nausea, lightheadedness, and other aches and pains are also possible as a result of the maximal effort exercise study. Although exercise testing may result in exhaustion, rarely do people develop abnormal heart rate or heart complications during exercise tests. The risk of this happening is the same as if the participant would exert themselves during stressful situations or during exercise elsewhere.

CONFIDENTIAL

We will perform ECG, heart rate, and blood pressures monitoring during our exercise test. In addition to the blood pressure (generally increases) and heart rate (generally increases) changes during exercise, we will also monitor arterial saturation. This will be done non-invasively using a pulse oximeter. Of note, oxygen levels can decrease with exercise, even in individuals without significant cardiopulmonary disease.¹³⁷ If the arterial saturation falls to below 88% ("severe exercise induced hypoxemia"¹³⁸), we will alert the patient's primary care provider as this may prompt consideration for additional or alternative causes for arterial hypoxemia.

Risks of FMD measurements: The cuff inflation used for FMD may cause temporary bruising. The inflation itself may cause tingling in the hand/digits, which resolves after deflation.

Risks of ambulatory blood pressure monitoring: There is minimal physical risk from non-invasive ambulatory blood pressure monitoring. A potential discomfort will be the squeezing from inflation of the blood pressure cuff, which may cause sleep disturbance for some participants.

Risks of SPPB: The gait and balance tests may lead to falls and the repeat chair stand test require a vigorous effort. However, these tests were found to be efficient, practical, and safe to administer to thousands of older persons in a home setting without any injury or adverse outcome.¹³⁹

Risks of impedance cardiography: this procedure is not associated with any known risks. Electrodes or electrode gel may cause irritation or itching.

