Main Inclusion and Exclusion Criteria	
Inclusion criteria:
 
• Subjects aged 18 years and older, male or female;• Prior diagnosis of COVID-19 (acute symptoms consistent with COVID-19, confirmed by PCR, serologic or rapid antigen test) for the COVID-19 survivors group, or no confirmed or suspected prior history of symptomatic COVID-19 for the control group at the time of enrollment. 
Exclusion criteria:
 
• Pregnancy at the time of the index COVID-19 episode or at the time of the first enrollment in the study; potential participants who become pregnant after the index COVID-19 episode will not be invited to participate until at least 3 months post-delivery. Inability to provide informed consent.• Known history of CVD (defined as HF, MI, coronary revascularization, serious arrhythmia, stroke, greater than moderate valvular heart disease, any cardiomyopathy, or PAD), glomerular disease or polycystic kidney disease prior to enrollment.• End stage kidney disease (ESKD; defined as requiring persistent renal replacement therapy or prior kidney transplant) prior to enrollment• History of chronic kidney disease (CKD) with eGFR <30 mL/min/1.73m² prior to enrollment. In participants without a history of CKD, a measurement of eGFR will not be required for enrollment.
--	---

CONFIDENTIAL

This material is the property of the University of Pennsylvania.

Study procedures	
• The phenotyping protocol will include brief questionnaires, a brief ultrasound examination, arterial tonometry, measurements of endothelial function, a 6-minute walk test, pulmonary function tests, Short Physical Performance Battery, impedance cardiography, blood, urine and breath condensate collection and 24-hour blood pressure monitoring. A subset of participants will be asked to complete a cardiopulmonary supine bike exercise test. All tests except for VO2 testing will be repeated at approximately 18-month intervals for a total of 3 tests

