3.3 Exclusion Criteria

- Pregnant women;
- Inability to provide informed consent.
- History of CVD (defined as HF, MI, coronary revascularization, serious arrhythmia, stroke, greater than moderate valvular disease, any cardiomyopathy, or PAD), glomerular disease or polycystic kidney disease prior to enrollment.

CONFIDENTIAL

- End stage kidney disease (ESKD; defined as requiring persistent renal replacement therapy or prior kidney transplant) prior to enrollment
- History of chronic kidney disease (CKD) with eGFR <30 mL/min/1.73m² prior to enrollment. In participants without a history of CKD, a measurement of eGFR will not be required for enrollment.

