Pulmonary Function Testing: We will perform a basic expired spirometry and measurements of CO diffusion capacity (DLCO) and lung volumes.⁶⁷ We will utilize an FDA-approved Easyone Pro Lab Respiratory Analysis System (NDD systems Andover, Massachusetts; 510K K161534). In this test, subjects perform a forced expiration into a disposable probe meter (spirometry), primarily to determine forced vital capacity and forced expiratory capacity in 1 s (FEV1). As recommended, DLCO measurements will be performed in duplicate for enhanced accuracy. In these measurements, participants will inspire CO gas one deep inspiration, followed by an ~8-10 second breath-hold, as tolerated, followed by normal breathing into the disposable mouthpiece for ~2 minutes, during which the machine measures the washout time of CO from the alveoli. Lung volumes will be performed by measuring the washout time of inhalation of 100% oxygen.

CONFIDENTIAL

This test will in total ~20 minutes. Pulmonary function tests will not be performed if participants are receiving >2L/min of supplemental oxygen.

Aerobic capacity: In a subset of participants who agree to additional testing, have no contraindications to exercise testing (such elevated fall risk or severely elevated blood pressure >180/100) and contingent on availability of equipment, personnel and funding, we will use a supine bicycle exercise protocol in conjunction with expired gas analysis to assess oxygen consumption (VO_2) during exercise. This subset of subjects will perform a maximal exertion limited exercise test using a graded-exercise protocol. We will use a supine cycle ergometer designed for stress echocardiography (Stress Echo Ergometer 1505, Medical Positioning, Inc, Kansas City, MO). Subjects will undergo expired gas analysis with a Parvo Medics True One 2400 device (Parvo Medics, Sandy, UT) or equivalent. Resistance began at 15 W for 3 minutes, increasing to 25 W for 3 minutes, and then increasing by 25 W every 3 minutes thereafter. Breath-by-breath information will be recorded. We will use custom-designed software already developed in Matlab (MathWorks, Natick, MA) at our lab for offline processing and quantification of all exercise data.⁶⁸ All data quantification will be blinded to treatment. Given costs considerations and funding availability, we will offer this additional component to former participants of the FERMIN trial (NCT04517396) but can be expanded to other participants as additional funding becomes available.

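### Section 7.1 relies on non-revascularized myocardial ischemia being a study exclusion to protect bicycle-test participants, but neither exclusion list nor the named bicycle-test contraindications includes it

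*Combined protocol and SAP*

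**What the plan says.** The protocol touches on this in four places.

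- **Section 7.1 (Risks), exercise testing.** "Non-revascularized myocardial ischemia, which may increase the risk of complications during exercise testing, is an exclusion criterion for the study". The next sentence adds a further protection. It calls the test voluntary and says that it "will not be performed in any participants with a contraindication to exercise, such as elevated risk of falls (as assessed by the investigators"). The second example it gives is blood pressure that is severely raised. The same paragraph says: "These procedures will be performed by qualified personnel according to established American Heart Association Guidelines".
- **Synopsis, Main Inclusion and Exclusion Criteria.** The cardiac exclusion reads "Known history of CVD (defined as HF, MI, coronary revascularization, serious arrhythmia, stroke, greater than moderate valvular heart disease, any cardiomyopathy, or PAD").
- **Section 3.3 (Exclusion Criteria).** The cardiac exclusion reads "History of CVD (defined as HF, MI, coronary revascularization, serious arrhythmia, stroke, greater than moderate valvular disease, any cardiomyopathy, or PAD"). The remaining exclusions in both lists concern pregnancy, consent and kidney disease.
- **Section 3.6.1 (Visit 1), Aerobic capacity.** Those entering the exercise subset must "have no contraindications to exercise testing (such elevated fall risk or severely elevated blood pressure >180/100"). On intensity: "This subset of subjects will perform a maximal exertion limited exercise test using a graded-exercise protocol". On who is offered it: "we will offer this additional component to former participants of the FERMIN trial (NCT04517396) but can be expanded to other participants".

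**The concern.** Section 7.1 itself says that unrevascularized ischemia may make exercise testing more hazardous, and it offers the exclusion of such people as a reason to accept the risk. Coordinators normally screen from the eligibility section. If the criterion is not there, the safeguard described in the risk section may not be applied to the people it concerns.

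What is at stake is participant safety in a small group: people with known ischemia who have had neither an infarct nor a revascularization and who agree to exercise to their limit. The statistical analysis is not at stake.

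**Working it through.** No arithmetic is involved beyond counting. The check sets the relevant texts side by side.

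| Place | Form of the rule | Ischemia named? |
|---|---|---|
| 7.1, first sentence on ischemia | Declares it a study exclusion | Yes |
| Synopsis exclusions | Closed definition, 8 cardiovascular conditions | No (0 of 8) |
| 3.3 exclusions | Closed definition, same 8 conditions | No (0 of 8) |
| 3.6.1, Aerobic capacity | Open-ended, 2 examples | No (0 of 2) |
| 7.1, contraindication sentence | Open-ended, same 2 examples | No (0 of 2) |

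**Step 1. Is the eligibility list closed?** Yes. Both versions define cardiovascular disease by enumeration and do not introduce the list as examples. The eight entries are heart failure, infarction, coronary revascularization, serious arrhythmia, stroke, valve disease beyond moderate, cardiomyopathy and peripheral artery disease.

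**Step 2. Does any entry capture unrevascularized ischemia indirectly?** Only in part. Excluding prior infarction and prior revascularization removes much overt coronary disease. It does not remove a person with angina or demonstrated ischemia who has had neither. That person belongs to the group section 7.1 says is kept out.

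**Step 3. Follow that person through the protocol.**

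1. Under section 3.3 alone, the person is eligible.
2. For the bicycle test, the person must have no contraindication to exercise. This condition applies before the test. Because its wording is open-ended, an investigator can and probably would count ischemia, but it is not named.
3. Section 7.3 limits the offer of testing to those able to do it. It gives no further criterion.
4. Section 3.6.1 (Other data collection) provides for review of medical records and of available cardiac imaging, which could reveal ischemia. It does not say that the review comes before the exercise test.
5. ECG, heart rate, blood pressure and saturation monitoring (section 7.1) acts only once exercise has begun.

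**Step 4. How many people could this affect?** The person must have known ischemia, have none of the eight conditions, be offered the test (at first only former participants of one earlier trial, though this may widen), accept it, and not be stopped at items 2 to 4 above. The documents give no frequency for any of these, so no number can be computed.

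**The case against.** The best defence is that section 7.1 is current protocol text and says outright that the condition is excluded. Read as a whole, the protocol excludes the person, and what is missing is a transcription into two lists. Having no contraindication is already a condition of entry to the exercise subset. The two examples are only illustrations, so their silence on ischemia proves little. If the cited guidelines name ischemia, the practical gap could be close to nil; they are not available here.

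Most of this stands, and it fixes the size of the point. It does not remove the inconsistency. An eligibility criterion that appears only in the risk section can be missed by anyone screening from section 3.3, and section 7.1 presents the contraindication rule as an addition to the ischemia exclusion, not a replacement for it.

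Two stronger readings are tempting, and the documents do not support them.

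- A reader might infer that nothing stands between a person with ischemia and a maximal test. That is wrong. The contraindication rule applies before the test, section 7.1 itself flags ischemia as a hazard, guidelines apply, and record review is planned.
- A reader might also infer an error from the 6-minute walk test, which section 3.6.1 protects with a screen for exertional and worsening chest pain, while the more demanding bicycle test has no such named screen. The contrast is fair, but the protocol never promises that screen for the bicycle test. Extending it would be an improvement and would not correct the mismatch.

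**Conclusion.** The point holds as a minor internal inconsistency with a limited safety consequence. Section 7.1 relies on an exclusion that appears in neither of the two exclusion lists and among neither of the two example contraindications. Screening from section 3.3 alone would admit people with known unrevascularized ischemia and none of the eight listed conditions.

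The mismatch in wording is certain. The practical effect is probably small and cannot be quantified from the documents, because it depends on guideline content that is not reproduced and on investigator judgement. The test is optional and done only at baseline. No estimate, endpoint or power figure is affected.

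The documents do not settle which section is wrong. The only intent they express is the whole-study exclusion in section 7.1, so one should not assume that this sentence is the mistake.

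**What to change.** **At minimum,** add known non-revascularized myocardial ischemia to the named bicycle-test contraindications in sections 3.6.1 and 7.1, and state that it is checked before the test by asking the participant and looking at available records. The participant's own history matters because section 3.4 allows recruitment through advertisements, and such people may have no local record. The cost is a short amendment and one line on a pre-test checklist.

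**Then make section 7.1 agree with the eligibility criteria,** in one of two ways:

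- If a whole-study exclusion is intended, add the condition to section 3.3 and the synopsis. The cost is that these people leave the cohort altogether: all 16 measure groups listed in section 3.1, all 3 visits and event follow-up.
- If protection of the exercise test is all that is intended, reword section 7.1 to call the condition a bicycle-test contraindication only. The cost is possibly a few fewer optional tests. An affected person loses 1 of the 16 measure groups and stays in the study for the rest.

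**Optional:** extend the chest-pain screen used for the 6-minute walk to the bicycle test. This is sensible for a maximal test, but it is a separate choice for the sponsor.

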7.2 Benefits

There may be no direct benefit to subjects as a result of their participation in the study. However, society in general may benefit as a result of scientific discoveries obtained during the course of this study. However, this study may provide novel information leading to the discovery and better understanding of long-term complications in COVID-19 survivors, which may in turn lead to newer approaches for their treatment or prevention. Results of research procedures will be shared with the patient or his/her providers upon request.

7.3 Informed Consent Process / HIPAA Authorization

All subjects for this study will be provided with an IRB-approved consent form providing sufficient information for subjects to make an informed decision about their participation in this study. The formal consent of a subject, including signing the IRB-approved consent form, will be required before that subject undergoes any study procedure. Participants able to perform exercise testing will be offered the option to undergo VO₂ testing.

7.4 Reporting of Incidental Findings

The tests in this study will be quantified for research purposes and not for clinical interpretation purposes. However, when incidental findings are encountered in study procedures, the study PIs will communicate these to study subjects and providers as necessary, based on their clinical judgement. These findings include but are not limited to, pulmonary function testing results and abnormalities discovered during ultrasound acquisition. If a PI is unable to contact a subject via phone, they may choose to mail a letter or send a message via MyPennMedicine.

CONFIDENTIAL

8 Study Finances

8.1 Funding Source

This study will be funded by the Investigators' discretionary funds. NIH funding will also be pursued.

